## STUDY SUMMARY

StudyTitle	STARTRIGHT: Getting the right classification and treatment from diagnosis in adults with diabetes
Internal ref. no. (or short title)	CRF243 (StartRight Study)
Study Design	Prospective observational
Study Participants	Adults who have been diagnosed with diabetes (excluding gestational or secondary diabetes) for $\leq 1$ year at the time of study recruitment. Aged $\geq 18$ at the time of diabetes diagnosis.
Planned Sample Size	Main cohort: 1000 Additional late onset diabetes cohort: 800
Follow up duration	3 years
Planned Study Period	6 years
Study Summary	This study aims to achieve more accurate early classification of diabetes and identification of which patients will rapidly require insulin treatment. We will recruit 1200 participants who have been diagnosed with diabetes in the last year and were aged between 18 and 50 years at the time of diagnosis. We will recruit an additional cohort of 800 participants diagnosed after age 50. We will record clinical features and biomarkers that may help us to determine diabetes type at diagnosis and follow participants for 3 years to assess the development of severe insulin deficiency (measured using C-peptide) and insulin requirement. We will assess utility of clinical features and additional biomarkers in identifying patients with rapid progression to insulin requirement. Findings will be integrated into a freely available clinical prediction model.

## FUNDING AND SUPPORT IN KIND

FUNDER(S)	FINANCIAL AND NON FINANCIAL SUPPORT GIVEN

National Institute for Health Research (NIHR Clinician Scientist award CS-2015-15-018): Integrating clinical features and biomarkers to improve diabetes classification and treatment in young adults. (<math>\leq</math> age 50 cohort)
 
Diabetes UK (17/0005624) Combining Clinical Features and biomarkers to identify patients with Type 1 diabetes in later life (<math>></math> age 50 cohort)
	
Financial: NIHR £866,655, Diabetes UK £366,766

NIHR Exeter Clinical Research Facility and NIHR Clinical Research Network
	
Support Infrastructure

Research & Development Directorate, Royal Devon & Exeter NHS Foundation Trust
	
Study Sponsorship and Research Governance Support

## ROLES & RESPONSIBILITIES:

### SPONSOR:

The sponsor has no role in the study design or data analysis, interpretation or manuscript writing. The sponsor will review and approve the study protocol and supporting documents. The sponsor takes overall responsibility for the study site monitoring that is carried out by the CI team.

### STEERING GROUP:

An independent steering committee will be appointed, made up of researchers, physicians and patients, to provide independent guidance and ensure that study progress and the conduct of the study is appropriate.

The steering committee will meet 6 monthly in the first year of the study, and annually thereafter, with the CI and members of the study team.

### STUDY MANAGEMENT:

Day to day management of the study will be undertaken by the CI and study coordinator with the support of the NIHR Exeter Clinical Research Facility.

**STUDY PROCEDURE SUMMARY FLOW CHART**

**NEWLY DIAGNOSED DIABETES PATIENTS IDENTIFIED IN PRIMARY OR SECONDARY CARE & SCREENED FOR ELIGIBILITY**

- Diagnosed with Diabetes in past 12 months
- Aged 18 or over at the time of diabetes diagnosis

**BASELINE RESEARCH VISIT & CONSENT (approx 30-45mins)**

- Blood & urine samples, clinical characteristics, treatment details, demographics & questionnaire
- Notes review by recruiting nurse to collect/confirm diagnosis details.
- Samples analysed for c-peptide & islet autoantibodies (GAD, IA2 & ZNT8), DNA, serum and plasma bio banked
- Clinician & participant informed of autoantibody results

**Follow Up 1 Year Post Recruitment**

- Contact (by phone, email, post or in person) to collect details of treatment change & hypoglycaemia
- Patient sends urine or blood sample by post to Exeter for UCPCR or serum C-peptide..
- Research team collects HbA1c results from GP practice or hospital records.

**Follow Up 2 Year Post Recruitment**

- Contact (by phone, email, post or in person) to collect details of treatment change & hypoglycaemia.
- Patient sends urine or blood sample by post to Exeter for UCPCR or serum C-peptide
- Research team collects HbA1c results from GP practice or hospital records.

**FINAL VISIT - 3 YEARS POST RECRUITMENT**

Repeat blood & urine samples, clinical characteristics, treatment details & questionnaire data collected at Visit 1.

## STUDY PROTOCOL

**StartRight: Getting the right classification and treatment from diagnosis in adults with diabetes.**

### 1 Lay summary

The treatment of Type 1 and Type 2 diabetes is very different. People with Type 1 diabetes rapidly stop making their own insulin, so need insulin injections from diagnosis. People with Type 2 diabetes can keep making their own insulin but it may not work as well as it should, so they can be treated with diet or tablets. While they may eventually need insulin treatment it is usually not until many years after diagnosis.

It is often difficult for doctors to tell which kind of diabetes a person has. Because of this, sometimes people are given the wrong diagnosis. This can have a huge impact as it means they could receive the wrong treatment. A person incorrectly diagnosed with Type 1 diabetes will be prescribed unnecessary insulin injections and miss out on other helpful therapies. A person incorrectly diagnosed with Type 2 diabetes may develop severely high glucose and become unwell with a condition called Diabetic Ketoacidosis if they do not receive insulin treatment.

This study aims to improve this situation by helping doctors more accurately tell the type of diabetes a person has when they are first diagnosed. We will recruit 1000 participants who have recently been diagnosed with diabetes between the ages of 18 and 50. We will recruit an additional 800 recently diagnosed participants who developed diabetes after age 50, half of whom will be receiving insulin therapy. We will record clinical features and measure blood tests that may help us determine diabetes type at diagnosis and follow participants for 3 years to see whether they stop producing their own insulin and need insulin treatment, which confirms Type 1 diabetes. We will assess whether clinical features and blood tests can help us tell if a patient needs rapid insulin treatment and should be initially treated as Type 1 or Type 2 diabetes.

We will combine results from this study and existing previous studies to produce a calculator, called a clinical probability model that will allow doctors and patients to combine information from clinical features and (where necessary) blood tests to accurately diagnose what type of diabetes a person has and therefore give the correct treatment. This will be freely available to doctors and patients as a website calculator and smartphone app.

### 2 BACKGROUND AND RATIONALE

#### **Correct diagnosis is needed for appropriate management of Type 1 and Type 2 diabetes**

Evidence based guidelines for the treatment of Type 1 and Type 2 diabetes are very different (1-4). These differences predominantly relate to the rapid development of severe insulin deficiency in Type 1 diabetes (3, 5). This means patients with type 1 diabetes need early insulin treatment, are at risk of life threatening ketoacidosis without insulin treatment and have poor response to non-insulin therapy(3). They require accurate insulin delivery (e.g. multiple injections, carbohydrate counting, pumps) due to the very high glycaemic variability associated with absolute insulin deficiency (5, 6). In contrast patients with Type 2 diabetes continue to produce substantial endogenous insulin even decades after

diagnosis (7). Glycaemia may therefore be initially managed with lifestyle change and non-insulin therapies, should insulin be required simple insulin regimens are combined with other agents (4, 8). Misdiagnosis will mean a patient receives inappropriate treatment, leading to unnecessary insulin therapy or, where Type 1 diabetes is misdiagnosed as Type 2, poor glycaemic control, potential ketoacidosis and earlier development of diabetes complications (9, 10).

### **Misclassification of diabetes is common and increasingly difficult in young adults**

BMI and age of diagnosis are usually used to differentiate diabetes subtypes however with increasing obesity Type 1 patients may be obese and Type 2 is seen in children and very young adults (11-13). Diagnosis on clinical features is therefore often difficult and initial misclassification is frequent (7-25%), particularly in young adults, an age group where incident Type 1 and Type 2 diabetes are both common (9, 14-16). In a recent study using similar definitions to this project, 26% of those treated with insulin from diagnosis and 23% of Type 2 diabetes diagnosed before age 35 were misclassified (17). Initial diagnosis is rarely revisited therefore misdiagnosis will have long term implications. A joint report by the Royal College of General Practitioners and NHS diabetes in 2011 highlighted the problems of misclassification of diabetes including a lack of clinical data and its importance from a clinician and patient perspective (9).

### **Half of older patients receiving insulin from diagnosis have been misdiagnosed**

Most patients developing diabetes after age 50 will have type 2 diabetes, therefore most patients (97%) of those treated as type 2 diabetes will be correctly classified. However we have recently shown that 49.5% of those treated as Type 1 diabetes (with insulin from diagnosis) after age 50 have been wrongly classified, as they continue to produce large amounts of their own insulin many years after diagnosis, confirming Type 2 diabetes (Jones et al unpublished, with misclassification 56% in a separate multicentre cohort (17)). This means that >6000 new patients annually in the UK in this age group are misclassified as having T1D, and consequently unnecessarily treated with insulin (18).

### **Robust evidence and guidelines for clinical classification of diabetes are needed**

We have systematically reviewed evidence on diabetes classification and found only 11 papers assessed clinical features against robustly defined diabetes subtypes with only 2 published in the last decade (19). No papers assessed young adult onset diabetes and only one assessed the utility of combining clinical features (20). While developments in assay technology have meant biomarkers such as C-peptide and autoantibodies are more robust and inexpensive there is a lack of evidence to support or refute their use, with the evidence quality for islet autoantibody testing to aid diabetes classification rated as low on expert committee review (21). Large prospective studies of mixed populations are needed to support or refute the use of these tests in clinical care.

### **Novel genetic biomarkers may improve diabetes classification**

The Exeter group have recently developed an inexpensive genetic risk score, based on 34 variants predisposing to Type 1 diabetes, which can discriminate Type 1 and 2 diabetes with AUC ROC 0.88 in cross-sectional datasets (22, 23). The score is independent and additive to autoantibody status and clinical features.

**A validated clinical probability model for diabetes classification has the potential to improve clinical care**

In many areas of clinical care decision making has been improved by using probability models ('calculators') that give appropriate weight to a multitude of patients features in a way that an individual clinician cannot (24). This approach has improved decision making in a wide range of conditions, for example physicians following NICE guidance for cardiovascular disease or osteoporosis will be familiar with the QRISK, GRACE and FRAX risk models. In response to widespread misdiagnosis of monogenic diabetes (25) the Exeter group has developed a probability model for common types of monogenic diabetes ('MODY') that outperforms standard clinical criteria (C statistic >0.94) (26). The resulting online calculator (<http://www.diabetesgenes.org/content/mody-probability-calculator>) has received 11900 visits in less than 2 years and is used prior to the majority of referrals for diagnostic genetic testing at the UK MODY referrals laboratory. It has recently been incorporated into an iphone app which aims to bring together current evidence and expert opinion to aid differential diagnosis of diabetes subtypes (Diabetes Diagnostics app). We are developing a model integrating clinical features to diagnosis diabetes subtype (Jones Shields unpublished) using cross sectional datasets which has not been prospectively tested. Simultaneous with the early stages of this study this model will be further developed using cross sectional cohorts in Exeter and Oxford.

### 3. OBJECTIVES AND OUTCOME MEASURES/ENDPOINTS

#### Primary objective

To establish diagnostic performance of biomarkers including islet autoantibodies, C-peptide and a genetic risk score in identifying patients with rapid requirement for insulin, alone and in combination with clinical features

#### Secondary objectives

To prospectively validate a clinical prediction model developed from cross sectional datasets in predicting rapid insulin requirement in young onset diabetes.

To integrate discriminative and additive biomarkers into the clinical prediction model.

To establish a bio resource for future biomarkers discovery and assessment.

#### Primary endpoint/outcome

Diabetes type defined by insulin requirement at 3 years:

Type 1 diabetes = Progression to insulin treatment and severe insulin deficiency (post meal plasma C-peptide <0.6nmol/L) at 3 years

Type 2 diabetes = Lack of requirement for insulin at 3 years (HbA1c <90mmol/mol without insulin treatment or post meal C-peptide  $\geq$  0.6nmol/L if insulin treated)

#### Rationale for primary outcome

A stimulated C-peptide less than 0.6nmol/L reflects severe insulin deficiency and is consistent with Type 1 diabetes outside the 'honeymoon' period and requirement for insulin treatment. A stimulated C-peptide over 0.6nmol/L represents substantial endogenous insulin secretion and is consistent with type 2 diabetes, non-insulin requirement and response to oral therapy, as reviewed in Jones 2013(27). Equivalent thresholds for fasting C-peptide and post meal urine C-peptide creatinine ratio have been derived from a dataset of 120 participants with insulin treated diabetes as previously reported (26). We have included early insulin treatment alongside measured insulin secretion as should an individual develop severe insulin deficiency at a late stage but have achieved glycaemic control without insulin for >3 years after diagnosis we would consider their initial treatment as Type 2 diabetes appropriate.

Where urine and blood C-peptide are discordant, classification will be based on the highest value. A cut off of 0.6nmol/mol will be used for classification based on urine C-peptide creatinine ratio (26).

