#### Secondary endpoints/outcomes

Stimulated C-peptide <0.2nmol/L at 3 years ('absolute insulin deficiency') (27, 28)

C-peptide rate of change (UCPCR and plasma)

HbA1c (mean and at 3 years)

Weight change (baseline to 3 years)

Self-reported hypoglycaemia & hypoglycaemic awareness (29, 30)

Wellbeing and resilience (SF12 and CD-RISC questionnaire) (30, 31)

Ketoacidosis (self-reported and confirmed from medical notes)

This research will produce a robustly validated clinical prediction model that will for the first time integrate validated clinical features and biomarkers to allow clinicians to accurately assess classification and need for insulin treatment at diabetes diagnosis. The model will be freely available to clinicians and patients through a website and smartphone App.

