#### 4. STUDY DESIGN

Prospective observational study. We will recruit a prospective cohort of 1200 adults diagnosed with diabetes within the previous 1 year and aged between 18 and 50 at the time of diagnosis.

We will also recruit an additional cohort of 800 participants diagnosed with diabetes in the last year aged >50 at diabetes diagnosis, with recruitment stratified by insulin treatment (400 insulin treated, 400 non insulin treated).

At baseline (visit 1) blood & urine samples will be collected for biomarker assessment and biobanking, and clinical features recorded. We will follow participants for 3 years with annual remote contact (phone, email or letter) and postal urine or capillary blood sample for C-peptide. A further face to face visit with blood & urine sampling will be performed at 3 years.

We will assess the utility of adding biomarkers to clinical features in diagnosing diabetes subtype (defined by insulin requirement at 3 years), and where utility is shown, integrate these into a probability model.

Please also refer to the study summary flow chart on page 7 for a summary of study procedures.

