### Patient burden:

Participation involves 2 blood samples (3 years apart) and 2 additional remote contacts (phone, email or letter according to participant preference) over the 3 year period. Participants will also collect a urine sample or capillary blood sample at home on 4 occasions.

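### The urine C-peptide creatinine ratio cut-off for the primary outcome is printed in nmol/mol, a unit that cannot match the 0.6 nmol/L plasma threshold; probably a misprint for nmol/mmol

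*Protocol*

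**What the plan says.** Section 3 of the protocol (Primary endpoint/outcome) defines Type 1 diabetes as "Progression to insulin treatment and severe insulin deficiency (post meal plasma C-peptide <0.6nmol/L) at 3 years". An insulin-treated participant at or above 0.6 nmol/L is Type 2.

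The Rationale for primary outcome extends this to other sample types: "Equivalent thresholds for fasting C-peptide and post meal urine C-peptide creatinine ratio have been derived from a dataset of 120 participants". It then fixes the urine value: "A cut off of 0.6nmol/mol will be used for classification based on urine C-peptide creatinine ratio". It also settles conflicts between samples: "Where urine and blood C-peptide are discordant, classification will be based on the highest value".

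The urine ratio (UCPCR) is named again in the flow chart, the secondary endpoints and sections 5.1.4 and 5.1.5, each time without a unit or a value. The line quoted above is therefore the only place that states the cut-off, and it is current text, not amendment history.

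**The concern.** Both cut-offs carry the number 0.6, one in nmol per litre of plasma and the other in nmol per mol of urinary creatinine. For these to mark the same level of insulin secretion, the kidney would have to clear C-peptide thousands of times more slowly than creatinine.

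This line decides outcome status. Diabetes type at 3 years is the reference standard for every sensitivity, specificity and prediction model in the study. A urine cut-off that is far too low pushes errors in one direction only. Under the highest-value rule, a urine result above the cut-off overrides a blood result below 0.6 nmol/L, so an insulin-treated participant moves from Type 1 to Type 2. Those participants come out of the smaller group on which the precision of sensitivity rests: by the inputs in section 9.1, 1000 × 0.80 × 0.25 = 200 in the younger cohort and 800 × 0.90 × 0.26 = 187 in the older one.

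**Working it through.** **Inputs from the protocol**
- Plasma threshold: 0.6 nmol/L, post-meal (Primary endpoint/outcome).
- Urine cut-off as printed: 0.6 nmol/mol (Rationale for primary outcome).
- Absolute insulin deficiency: stimulated C-peptide below 0.2 nmol/L (Secondary endpoints/outcomes).

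**Inputs assumed, not in the documents**
- Ratio *k* of C-peptide clearance to creatinine clearance: 0.005-0.30.
- Plasma creatinine: 0.05-0.12 mmol/L.

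The protocol shows no conversion from plasma to urine, so there is no figure of its own to reproduce.

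**Step 1. Unit conversion.** 0.6 nmol/mol ÷ 1000 = 0.0006 nmol/mmol.

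**Step 2. Urine ratio expected at the plasma threshold.** At steady state, UCPCR = *k* × plasma C-peptide / plasma creatinine.
- Lowest: 0.005 × 0.6 / 0.12 = 0.025 nmol/mmol.
- Highest: 0.30 × 0.6 / 0.05 = 3.6 nmol/mmol.

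**Step 3. Comparison with the printed value.** 0.025 / 0.0006 = 42 and 3.6 / 0.0006 = 6000. The printed cut-off is too low by at least about 40-fold across the whole range.

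**Step 4. What equivalence would require.** *k* = 0.0006 × (0.05 to 0.12) / 0.6 = 0.00005 to 0.00012, at least about 40 times below the bottom of the assumed range. Read as 0.6 nmol/mmol, the required *k* is 0.6 × (0.05 to 0.12) / 0.6 = 0.05 to 0.12, inside that range.

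**Step 5. Second set of assumptions, chosen separately.** C-peptide clearance 1-10 mL/min, creatinine clearance 60-140 mL/min, plasma creatinine 0.04-0.12 mmol/L.
- Lowest: 0.6 × 1 / (0.12 × 140) = 0.036 nmol/mmol.
- Highest: 0.6 × 10 / (0.04 × 60) = 2.5 nmol/mmol.
- Central (5 mL/min, 100 mL/min, 0.07 mmol/L): 0.6 × 5 / (0.07 × 100) = 0.43 nmol/mmol.

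Against 0.0006, these are about 60-fold, 4200-fold and 700-fold. The conclusion is the same.

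**Step 6. Plasma level at which the printed cut-off would be passed.** At the extreme least favourable to the concern: 0.0006 × 0.12 / 0.005 = 0.0144 nmol/L. That is a few per cent of 0.6 nmol/L and more than ten times below 0.2 nmol/L. Only the order of magnitude should be read from this.

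**Step 7. Consistency with the highest-value rule.** At plasma 0.6 nmol/L the urine number is about 0.025-3.6 in nmol/mmol, but about 25-3600 in nmol/mol. A rule that takes the higher value, with 0.6 as the cut-off on both scales, is workable in the first unit. In the second, the urine number would nearly always be the larger.

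**The case against.** **It is a one-letter slip that is unlikely to reach the analysis.** C-peptide is measured in a central laboratory under written procedures, and the protocol cites a source for the cut-off. An analyst with laboratory results in nmol/mmol and that source to hand would probably apply 0.6 nmol/mmol. This stands as a limit on the likely harm. It does not make the line right: no other place in the protocol would correct someone who follows it.

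**The mismatch rests on outside physiology.** True, and the formula is a steady-state one applied to post-meal samples. The ranges are wide for that reason, and the error would have to exceed a further factor of about 40 at the most favourable corner to rescue the printed unit. The order of magnitude stands; exact multiples do not.

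**The text was extracted from PDF.** Losing one letter from nmol/mmol would give exactly this string. That cannot be fully excluded. The HbA1c unit mmol/mol in the endpoint section came through intact, which makes it less likely.

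**A reader might infer that nearly all insulin-deficient participants would be classed Type 2.** The documents do not support that. It would need the distribution of C-peptide below 0.6 nmol/L and the share of participants with a urine result at 3 years, and neither is given. Urine at 3 years is planned in section 4 ("A further face to face visit with blood & urine sampling will be performed at 3 years") and in the flow chart ("Repeat blood & urine samples, clinical characteristics, treatment details & questionnaire data collected at Visit 1"), but section 5.1.6 lists only blood for that visit, and home urine may be replaced by capillary blood. Participants not on insulin are not reclassified by this rule at all.

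**Conclusion.** The concern holds. The printed urine cut-off of 0.6 nmol/mol cannot be equivalent to plasma 0.6 nmol/L. It is at least about 40-fold too low under the assumed clearance ratio (0.005-0.30) and plasma creatinine (0.05-0.12 mmol/L), and exactly 1000-fold too low if nmol/mmol was intended.

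A misprint for nmol/mmol is the probable explanation, since 0.6 nmol/mmol lies inside every range computed and fits the highest-value rule. It remains an inference, because the derivation data are not in the protocol.

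The consequence is conditional. Applied literally, the cut-off would move insulin-treated participants with a 3-year urine result to Type 2 at plasma levels far below the stated threshold, in numbers the documents do not allow one to estimate. If the laboratory and analysts already use nmol/mmol, no classification changes. Nothing in the protocol shows that a wrong cut-off has been or will be used. The confidence intervals in section 9.1 were not calculated from this unit. It should still be corrected before outcomes are classified, because it is a decision threshold of the primary outcome.

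**What to change.** Check the source file to rule out a reading error. Then check the urine cut-off and its unit against the cited derivation in 120 participants, reconcile them with the plasma threshold in the Primary endpoint/outcome section, and correct the unit in the Rationale for primary outcome (probably to nmol/mmol). Print the unit wherever a urine value is used for classification, and confirm that the laboratory's reporting unit and the analysis code agree with it.

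The cost is one source check and a one-line correction. Design, samples and visits do not change. If any outcomes have already been classified on urine results, confirm which unit was applied.
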